3.4 Primary Study Data Collected from Review of Clinical Records and Study Procedures

3.4.a: Medical History and Physical Examination: age, sex, history of hypertension, diabetes, hyperlipidemia, coronary disease, atrial fibrillation, pacemaker, myocardial infarction, chronic kidney disease, obesity (BMI ≥ 30), collagen vascular disease, lung disease (obstructive, restrictive), previous thoracic radiation or valve disease and blood pressure, heart rate, height, weight.

3.4.b: Laboratory values: creatinine, blood urea nitrogen, NT-proBNP, Hgb, Hct, platelets, white blood cells, and INR day of or day before procedure (only if on warfarin and holding for EMB).

3.4.c: Electrocardiogram: rate, rhythm (sinus, atrial flutter or AF, ventricular pacing), QRS duration, LBBB pattern (yes/no)

3.4.d: Echocardiogram: Left atrial dimension and/or volume (method), LV end diastolic dimension and/or volume (method), LV septal and posterior wall thickness, LV ejection fraction (value/method), right ventricular size (semiquantitative) and function (semiquantitative), aortic, mitral, tricuspid and pulmonary valve function (stenosis or regurgitation grade)

3.4.e: Resting hemodynamics: HR, systemic blood pressure, RA (a,v,mean), RV (systolic, end-diastolic), PA (systolic, diastolic, mean), PCWP (a,v, mean), cardiac output method (Fick indirect, Fick direct, thermodilution), cardiac output, cardiac index, PVR, PA compliance.

3.4.f: Passive Leg Raise hemodynamics: PCWP (a,v, mean)

3.4.g: Clinically indicated exercise hemodynamics (if performed): Exercise method (arm, bike upright, bike supine, other), peak level (watts, other), and same hemodynamic measures as in 3.4.e (as available).

3.5 Primary Safety Data Collected

3.5.a: Pre-EMB echo: Echocardiographic tricuspid regurgitation grade (semi-quantitative) and pericardial effusion (window, dimension)

3.5.b: Immediate post-EMB echo: Echocardiographic tricuspid regurgitation grade (semi-quantitative) and pericardial effusion (window, dimension), tamponade physiology (yes/no)

3.5.c: Research RHC complications: death, chest pain, hemoptysis, pneumothorax, access site bleeding or hematoma exceeding usual expected severity, new atrial fibrillation/flutter, other clinically significant arrhythmias (ventricular tachycardia requiring therapy, heart block requiring therapy), pulmonary artery perforation, new or worsening tricuspid regurgitation.

3.5.d: Research EMB complications: death, chest pain, hemoptysis, pneumothorax, access site bleeding or hematoma exceeding usual expected severity, new atrial fibrillation/flutter, other clinically significant arrhythmias (ventricular tachycardia requiring therapy, heart block requiring therapy), new or worsening tricuspid regurgitation, new pericardial effusion requiring admission or serial echocardiography without intervention, tamponade requiring percutaneous pericardiocentesis, tamponade requiring surgical pericardiocentesis with or without myocardial repair.

4.0 STUDY PROCEDURES

4.1 Right Heart Catheterization (RHC)

Right heart catheterization will be performed as previously described.⁷² Prior to cardiac catheterization, an IV cannula will be inserted in a forearm vein for fluid and medication administration. Vascular access is accomplished using ultrasound imaging and local anesthesia. A 9 Fr sheath is deployed under local anesthesia in the right internal jugular vein, and an optional 4 Fr cannula is placed in the radial artery to sample arterial blood and measure blood pressure (if performing Fick cardiac outputs). If left heart catheterization is to be performed for clinical purposes (requiring a larger arterial sheath), EMB will be completed prior to arterial puncture owing to the need to administer heparin following arterial access. A flow guided balloon PA catheter is placed via the jugular venous sheath with or without a micromanometer tipped catheter wire for measurement of fluid filled and/or high-fidelity pressure waveforms in the RA, RV, PA and PCWP positions, all following EMB.

Hemodynamics and cardiac output at rest and during exercise (if indicated) will be measured using gold standard invasive techniques in patients with HFpEF.⁷² Resting oxygen consumption and mixed venous and arterial blood samples will be obtained at rest and during exercise (if performed) for Fick calculated cardiac output (if performed).

Passive Leg Raise: As previously described⁷³, during the passive leg raise maneuver, the legs of the patients should be raised by staff lifting the patients feet so that the legs form an angle of \approx 50 degrees to the cath lab table. During this maneuver, the patient should be explicitly instructed to relax his/her legs and not to help so as to avoid a Valsalva maneuver. If the patient is to undergo supine bicycle exercise, the feet can be placed in the supine bike pedals which will maintain the \approx 50 degree angle. The patient should again be encouraged to relax leg muscles and breath normally. After two minutes of elevation by holding legs or putting feet on the bike pedals, the PCWP should be measured as the average of at least 3 beats.

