3. STUDY DESIGN

3.1 General Description:

Patients will be consented for research RHC (if not planned for clinical purposes; 4.1 Study Procedures - RHC) and/or research EMB. Within six months of participation, patients will have had a clinically indicated transthoracic echocardiogram, NT-proBNP level, complete blood count, basic metabolic panel and electrocardiogram and/or will have these as research studies as part of this study or the Heart Share Deep Phenotyping Protocol (section 3.4).

Patients will initially be classified as “known HFpEF” or “suspected HFpEF” per criteria below (3.2 Study Population). If the patient has known HFpEF or if the patient meets resting hemodynamic criteria ($_{REST}PCWP \geq 15$ mmHg) for HFpEF, the patient will have confirmed HFpEF and the research EMB will be performed (Figure).

If the patient has suspected HFpEF and does not meet resting hemodynamic criteria for HFpEF, the risk of HFpEF will be assessed (Figure).

If the risk of HFpEF is high as evidenced by a H2FpEF score ≥ 3 or a passive leg raise (PLR) PCWP ≥ 18 mmHg, the patient will undergo research EMB. As clinical studies indicate that these patients have impaired functional capacity and increased risk of future HF,^{67,68} they will be classified as pre-HFpEF unless clinically indicated exercise hemodynamic assessment meets criteria for HFpEF (Figure).

If the patient has low risk of HFpEF based on the H2FpEF score or the $_{PLR}PCWP$, the patient does not qualify for research EMB and is classified as “not HFpEF” unless clinically indicated exercise hemodynamic assessment meets criteria for HFpEF (rare).

The research EMB (4.2 Study Procedures – EMB) will be performed using fluoroscopic or echocardiographic guidance per operator preference. If an EMB is indicated clinically, the three research EMB will be performed after the clinical EMB (usually 3-5 biopsies, per clinician specifications) have been obtained. Before and immediately after the research EMB, transthoracic echocardiographic assessment of tricuspid valve structure and regurgitation and pericardial fluid will be performed and findings recorded, along with blood pressure and heart rate.

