After the research EMB and post-EMB imaging, other clinically indicated procedures (i.e. exercise hemodynamics, drug studies for pulmonary vascular function) to further evaluate HFpEF will be performed. Patients may participate in other research protocols as long as the studies do not interfere with the study entry algorithm (figure) and the ability to perform the EMB.

After the research EMB and any other clinically indicated procedures, patients will be observed for clinical stability in the catheterization laboratory post procedural area and then discharged according to routine post-procedural practice at the participating site. At discharge and at 30 days post procedure, the clinical record will be reviewed, and a case report form completed documenting any procedural related adverse events due to research RHC or EMB.

Up to 300 patients will be enrolled over a five-year period at up to 10 sites participating in the MM-HFpEF study.

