3.2 Study Population

3.2.a: Inclusion criteria: Patients with known or suspected HFpEF will be identified by electronic medical record searches, referrals from clinicians, focused screening in the clinical practice including patients scheduled for RHC to diagnose or assess severity of HFpEF, responses to posting of research opportunities or review of patient lists from previous HFpEF studies.

HFpEF criteria

1. Age ≥ 30 years.
2. Left ventricular ejection fraction $\geq 50\%$ measured by echocardiography, CMR or MUGA (measured within one year + clinical stability)
3. Definition of HFpEF: signs and/or symptoms of HF, NYHA functional class II-IV, and at least one of the following:
 - a. Elevated BNP (≥ 75 pg/ml in sinus rhythm or ≥ 225 pg/ml in atrial fibrillation/flutter) or NTproBNP (≥ 225 pg/ml in sinus rhythm or ≥ 675 in atrial fibrillation/flutter) at baseline. Choice of BNP or NTproBNP is based on availability at each clinical center.
 - b. Prior HF hospitalization (primary reason for the hospitalization is HF with elevated natriuretic peptide levels [using the thresholds listed above], requiring IV diuresis for HF, or pulmonary edema or pulmonary vascular congestion on chest radiography).
 - c. Previously documented elevated pulmonary capillary wedge pressure (PCWP) at rest (≥ 15 mmHg) or during exercise (≥ 25 mmHg for supine exercise or PCWP/cardiac output ratio ≥ 2 mmHg/L/min for upright exercise).
 - d. Elevated H₂FPEF score⁶⁹ (≥ 5) or HFA-PEFF⁷⁰ score (≥ 5).

Suspected HFpEF criteria

1. Age ≥ 30 years.
2. Left ventricular ejection fraction $\geq 50\%$ measured by echocardiography, CMR or MUGA (measured within one year + clinical stability)
3. Signs and/or symptoms of HF, NYHA functional class II-IV and all of the following:
 - a. Does not meet BNP or NT-proBNP criteria for HFpEF (above)
 - b. No prior HF hospitalization meeting HF criteria (above)
 - c. No previous hemodynamic catheterization documentation of HF (as above)

3.2.b: Exclusion criteria:

According to current guidelines,⁷¹ patients deemed at increased risk of right ventricular (RV) septal EMB complications as evidenced by any of the below will be excluded.

1. Inadequate echo or fluoroscopic images.
2. Neck anatomy unfavorable for jugular venous cannulation
3. Therapy with direct oral anticoagulants without cessation for a period (age, renal function, and agent specific) deemed adequate to normalize coagulation according to local clinical guidelines.

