4.2 Endomyocardial biopsy (EMB)

After resting hemodynamics and baseline echocardiographic imaging for tricuspid valve structure and regurgitation and pericardial effusion is performed, a bioptome will be passed via the venous sheath. Three EMB will be performed under fluoroscopic or echocardiographic guidance according to recommendations of the joint European Society of Cardiology (ESC) Heart Failure Association, Heart Failure Society of America and Japanese Heart Failure Society Position Statement on EMB (2021).⁷¹ To minimize risk, operators will need to have averaged at least 20 to 50 RV EMB per year⁷¹ for at least the preceding four years (exclusive of COVID impact in 2020). Continuous electrocardiographic and pulse oximetry monitoring and intermittent blood pressure (if no arterial line used) will be monitored. Echocardiographic assessment for tricuspid valve structure and regurgitation and for pericardial effusion is briefly assessed during each biopsy and at the end of the procedure. After the research EMB, patients are observed for clinical stability in the catheterization laboratory post procedural unit for at least 2 hours prior to discharge. Repeat echo imaging of tricuspid valve structure and regurgitation and for pericardial effusion will be performed in the post-procedural unit prior to discharge.

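### Section 4.1 puts all right-heart pressures, including PCWP, after the biopsy, but sections 3.1 and 4.2 need resting PCWP before it, and for some suspected patients PCWP decides whether a biopsy is allowed

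*Protocol*

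**What the plan says.** Three sections set the order of pressure measurement and biopsy.

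- **Section 4.1 (RHC)** describes placing the pulmonary artery catheter "for measurement of fluid filled and/or high-fidelity pressure waveforms in the RA, RV, PA and PCWP positions, all following EMB". The sentence carries no condition and covers every right-heart pressure position. The leg-raise paragraph later in 4.1 does not say whether the manoeuvre comes before or after the biopsy.
- **Section 4.2 (EMB)** begins "After resting hemodynamics and baseline echocardiographic imaging for tricuspid valve structure" and only then introduces the bioptome. It does not mention the leg raise.
- **Section 3.1 (General Description)** sets the entry algorithm. Known HFpEF, or a resting PCWP of at least 15 mmHg, leads to biopsy. A suspected patient below that threshold is biopsied if there is "a H2FpEF score ≥ 3 or a passive leg raise (PLR) PCWP ≥ 18 mmHg". A low-risk patient is handled differently: "the patient does not qualify for research EMB". Those biopsied on the risk criteria carry a separate label: "they will be classified as pre-HFpEF unless clinically indicated exercise hemodynamic assessment meets criteria for HFpEF".

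Section 3.1 also names what comes later: "After the research EMB and post-EMB imaging, other clinically indicated procedures (i.e. exercise hemodynamics, drug studies for pulmonary vascular function". Resting and leg-raise pressures are not on that list.

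Section 3.2.a defines known HFpEF as "signs and/or symptoms of HF, NYHA functional class II-IV, and at least one of the following", the list being natriuretic peptides, prior HF hospitalization, earlier documented PCWP elevation, and an H2FpEF or HFA-PEFF score of 5 or more. Suspected patients have, by definition, no earlier catheterization that documented HF.

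**The concern.** A measurement that decides whether a procedure is permitted has to be available before the procedure. Section 4.1, the section a catheterization team would consult, says it comes afterwards. Two things are at stake.

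1. **Eligibility.** The biopsy is invasive and done for research, and the protocol's ethics section says participants should expect no direct benefit. The rule that keeps low-risk people from being biopsied depends on PCWP in part of the suspected group. If PCWP is read only after the biopsy, the rule cannot work for them.
2. **Classification.** In suspected patients, resting PCWP separates confirmed HFpEF from pre-HFpEF. Under 4.1 that reading follows the intervention. The biopsy complications listed in section 3.5.d include "new or worsening tricuspid regurgitation, new pericardial effusion requiring admission or serial echocardiography without intervention, tamponade requiring percutaneous pericardiocentesis", events that could alter a later pressure reading. Because the study compares clinically defined groups, the label should rest on a pre-biopsy value.

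**Working it through.** No sample size, power or error-rate figure is involved. The check traces the 3.1 algorithm through each type of patient to see where the biopsy decision needs a PCWP from the current procedure.

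| Status | H2FpEF score | Resting PCWP (mmHg) | Leg-raise PCWP (mmHg) | Biopsy under 3.1 | Label | PCWP needed to allow biopsy? |
|---|---|---|---|---|---|---|
| Known HFpEF | any | any | any | yes | confirmed HFpEF | no |
| Suspected | 3 or more | 15 or more | not needed | yes | confirmed HFpEF | no, label only |
| Suspected | 3 or more | below 15 | not needed | yes | pre-HFpEF | no, label only |
| Suspected | below 3 | 15 or more | not needed | yes | confirmed HFpEF | **yes** |
| Suspected | below 3 | below 15 | 18 or more | yes | pre-HFpEF | **yes** |
| Suspected | below 3 | below 15 | below 18 | no | not HFpEF | **yes** |

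The pre-HFpEF and not-HFpEF labels hold unless clinically indicated exercise testing meets HFpEF criteria. A patient with an H2FpEF score of 5 or more who meets the other entry conditions counts as known HFpEF under 3.2.a, so the second and third rows mainly concern scores of 3 and 4.

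In the last three rows PCWP alone decides. The qualifying value has to come from the current catheterization, since a suspected patient has no earlier qualifying one. Under 4.1 it would exist only after the tissue had been taken.

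The exercise exception does not rescue the order. Section 3.1 calls it rare, it may attach to the label and not to the permission, and 3.1 places exercise testing after the biopsy.

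**How often a complication could disturb a post-biopsy PCWP.** Section 4.4 puts tamponade and ventricular arrhythmia each below 2 per 1000 procedures at two participating hospitals. With the planned maximum of 300 patients:

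- 300 × 2/1000 = 0.6, so fewer than 0.6 patients for each event.

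This assumes all sites match those two hospitals. The section 4.4 table gives a wider range for tamponade or hemopericardium. Apart from one study at 6.9%, the listed rates run from 0.05% to 1.5%:

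- 300 × 0.0005 = 0.15 and 300 × 0.015 = 4.5 patients.
- At 6.9%: 300 × 0.069 = 20.7 patients.

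For tricuspid regurgitation, the table lists 0.02% to 1.1%, and one centre's series found worsening in 5.1% of biopsies, mostly asymptomatic and mostly in transplant patients:

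- 300 × 0.0002 = 0.06, 300 × 0.011 = 3.3 and 300 × 0.051 = 15.3 patients.

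These are counts of events, not of altered PCWP readings. The protocol does not quantify the effect of either event on PCWP, and the label is at risk only in the suspected patients among the 300.

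**The case against.** The strongest reply is that 4.1 describes technique and gives no permission to biopsy. Permission comes only from 3.1. A suspected patient scoring below 3 with no PCWP yet has met no entry criterion, so reading 4.1 and 3.1 together produces a deadlock, not an unauthorised biopsy. A site would have to disregard 3.1 and the order in 4.2 to cause harm. This is largely right, and it is why the point is a correction to make and not a fatal flaw. It does not remove the conflict: a procedure section that cannot be followed alongside the entry algorithm leaves up to 10 sites to choose between them.

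A second reply is that the phrase belongs to the preceding sentence in 4.1, which puts biopsy before arterial puncture when left heart catheterization is planned. That sentence has its own condition and the catheter sentence has none. Even if limited to those cases, the phrase would still conflict with 4.2 and with the entry rule. The heparin rationale requires biopsy before arterial puncture, not before venous pressure measurement.

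Third, section 3.3 mentions other RHC measurements after the biopsy. That fits exercise and other later studies and does not require resting PCWP to wait.

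Fourth, the entry figure, which is not in the copy reviewed, may show the leg raise before the biopsy. That is possible, and 3.1 already implies that order by making biopsy depend on the result. The figure would not cancel the words in 4.1.

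Finally, the complication argument is thin. This stands in part: serious events are expected to be rare, their effect on PCWP is not quantified, and the immediate post-biopsy echocardiogram would record effusion, tamponade or worse regurgitation. Classification is therefore the lesser concern.

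**Conclusion.** The contradiction is real and stands in the current operative text. Section 4.1 is wrong as written, and the order in 3.1 and 4.2 is the one the design needs.

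The eligibility consequence is limited to suspected patients with an H2FpEF score below 3. Its size cannot be stated without the share of suspected patients and the share of them scoring below 3, and the protocol gives neither. Whether anyone is wrongly biopsied depends on a site following 4.1 over 3.1 and 4.2. For suspected patients scoring 3 or more, only the confirmed versus pre-HFpEF label is exposed. Known HFpEF patients are unaffected on both counts.

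This should be fixed because it concerns the order of an invasive research procedure and the condition that restricts it, and because correcting it costs almost nothing.

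**What to change.** Amend 4.1 to say that resting right-heart pressures and, where the 3.1 algorithm needs it, the leg-raise PCWP are measured before the biopsy. Limit the post-biopsy timing to exercise and the other clinically indicated measurements that 3.1 already places there. Keep the rule that biopsy precedes arterial puncture for left heart catheterization. Section 3.3 needs no change.

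The cost is a one-phrase wording correction, with no added patients, procedures or data fields.

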4.2 Endomyocardial biopsy (EMB)

After resting hemodynamics and baseline echocardiographic imaging for tricuspid valve structure and regurgitation and pericardial effusion is performed, a bioptome will be passed via the venous sheath. Three EMB will be performed under fluoroscopic or echocardiographic guidance according to recommendations of the joint European Society of Cardiology (ESC) Heart Failure Association, Heart Failure Society of America and Japanese Heart Failure Society Position Statement on EMB (2021).⁷¹ To minimize risk, operators will need to have averaged at least 20 to 50 RV EMB per year⁷¹ for at least the preceding four years (exclusive of COVID impact in 2020). Continuous electrocardiographic and pulse oximetry monitoring and intermittent blood pressure (if no arterial line used) will be monitored. Echocardiographic assessment for tricuspid valve structure and regurgitation and for pericardial effusion is briefly assessed during each biopsy and at the end of the procedure. After the research EMB, patients are observed for clinical stability in the catheterization laboratory post procedural unit for at least 2 hours prior to discharge. Repeat echo imaging of tricuspid valve structure and regurgitation and for pericardial effusion will be performed in the post-procedural unit prior to discharge.

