4.5 Strategies to mitigate Risk to Participants

To minimize risk, operators will need to have averaged at least 20 to 50 RV EMB per year⁷¹ for at least the preceding four years (exclusive of COVID impact in 2020). Continuous electrocardiographic and pulse oximetry monitoring and intermittent blood pressure (if no arterial line used) will be monitored. Echocardiographic assessment for tricuspid valve structure and regurgitation and for pericardial effusion is assessed during each biopsy and at the end of the procedure. After the research EMB, patients are observed for clinical stability in the catheterization laboratory post procedural area as per local clinical protocols and as deemed necessary by the EMB operator. Repeat echo imaging of tricuspid valve structure and regurgitation and for pericardial effusion is performed immediately after the procedure in the catheterization laboratory. Only RV EMB will be performed (lower risk of stroke and arterial bleeding). Only clinically stable patients without high-risk features (see **3.2.b: Exclusion criteria**) will be included.

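### Sections 4.2 and 4.5 (risk mitigation) give conflicting rules after the research biopsy: 4.5 drops the 2-hour minimum observation and the pre-discharge echo

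*Protocol*

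**What the plan says.** Section 4.2 (Endomyocardial biopsy) has three elements after the biopsy begins. Echo for the tricuspid valve and pericardial effusion "is briefly assessed during each biopsy and at the end of the procedure". The patient is then observed in the "post procedural unit for at least 2 hours prior to discharge". A repeat echo "will be performed in the post-procedural unit prior to discharge".

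Section 4.5 (Strategies to mitigate Risk to Participants; a second section, on tissue analysis, carries the same number) repeats most of that paragraph. Echo "is assessed during each biopsy and at the end of the procedure". Observation, however, is in the "post procedural area as per local clinical protocols and as deemed necessary by the EMB operator", and the repeat echo "is performed immediately after the procedure in the catheterization laboratory".

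Section 3.1 names 4.2 as the biopsy procedure. It asks for an echo immediately after the biopsy and then allows other clinically indicated procedures. On what follows it says: "After the research EMB and any other clinically indicated procedures, patients will be observed for clinical stability"; they are "then discharged according to routine post-procedural practice at the participating site".

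**The concern.** The biopsy is taken for research, and the protocol expects no direct benefit to the participant. Its risk-benefit statement rests on the risk being low, and 4.5 is the section that explains how risk is kept low. That section carries the weaker rule.

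The immediate scan is not the last event of the day for every patient. Exercise hemodynamics or drug studies may follow it. If a clinical left heart catheterization is planned, 4.1 puts the biopsy before arterial puncture, so heparin is given after the biopsy. An effusion that appears after the immediate scan would be looked for before discharge under 4.2 but not necessarily under 4.5. With up to 10 sites, practice could differ between sites, and monitors checking compliance would have two standards.

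**Working it through.** The protocol states no figure to reproduce here, so the check compares the texts and then puts a rough ceiling on the size.

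**Step 1. The two conflicting sections.**

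| Element | 4.2 | 4.5 (risk mitigation) |
|---|---|---|
| Echo during biopsies and at end of procedure | Yes | Yes |
| Minimum observation | 2 hours | None; local protocol and operator |
| Place of repeat echo | Post-procedural unit | Catheterization laboratory |
| Time of repeat echo | Before discharge | Immediately after the procedure |

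The first row agrees and the other three do not. Discharge at 60 minutes after only an immediate scan would satisfy 4.5 and breach 4.2.

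**Step 2. Do other sections settle it?**

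- 3.1 cites 4.2 for the biopsy, which favours 4.2 but is not a precedence clause. It places observation after any later procedures, without repeating the 2 hours or the pre-discharge scan.
- 3.3 estimates participant time. For research catheterization plus biopsy it gives 4 to 8 hours in total and 30 to 90 minutes for the procedure. The shortest day then leaves 4 − 1.5 = 2.5 to 4 − 0.5 = 3.5 hours for registration, preparation and monitoring together. That is compatible with a 2-hour stay but does not require one.
- 3.5.b lists the immediate post-biopsy echo as a primary safety item. It is a data list and sets no bedside rule.

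None of these removes the conflict in step 1.

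**Step 3. Size.** Expected events = number of patients × event rate, with the planned maximum of 300 patients.

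- Core Laboratory rate of effusion needing pericardiocentesis, 0.06% (section 4.4): 300 × 0.0006 = 0.18.
- Tamponade below 2 per 1000 in the two participating-hospital series (section 4.4): 300 × 0.002 = 0.6, so fewer than 0.6.
- Section 4.4 table, hemopericardium or tamponade, ten series. Nine run from 0.05% to 1.5%: 300 × 0.0005 = 0.15 to 300 × 0.015 = 4.5. The tenth, at 6.9%, gives 300 × 0.069 = 20.7.

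These counts cover events at any time and at all sites. The cases at issue are the subset that appears after the immediate scan, at sites following 4.5, where local practice is shorter than 2 hours or includes no later scan. The protocol does not split its rates by time of detection and does not describe local practice, so that subset cannot be computed.

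**The case against.** The strongest reply is that the sections can be satisfied together. Nothing in 4.5 forbids a 2-hour stay or a second scan, and a site applying the strictest text would meet every section. Section 4.2 is the procedure section, and 3.1 sends the reader there. This stands as a limit on the likely harm. It does not remove the conflict, because 4.5 describes the same repeat echo at a different time and place, and no clause tells a site to take the stricter text.

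A reader might infer that 3.1 also contradicts 4.2. It does not: discharge by site routine can sit on top of a 2-hour floor. A reader might also count 3.3 and 3.5 as further sections that lack the rule. That would inflate the point, since one is a time estimate and the other a data list.

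A third tempting inference is that late complications would go unrecorded. The documents do not support it. Section 3.5.d captures new or worsening regurgitation, and effusion or tamponade needing action. Adverse events are recorded for 30 days, and the clinical record is reviewed at discharge and at 30 days. The case report forms are not shown, so a missing field cannot be established. What these safeguards do not supply is a scan before the patient leaves.

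On heparin, the order in 4.1 is itself a precaution, since it avoids taking biopsies under heparin. It does not provide a later scan.

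Finally, nothing proves that 4.2 is the intended rule. Choosing it is a judgement: it is the stricter text, it is already a requirement, and it is the section 3.1 cites.

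**Conclusion.** The conflict between 4.2 and 4.5 is real and should be corrected. It concerns two bedside safety rules: the minimum observation time, and the timing and place of the repeat echo. Section 3.1 merely fails to repeat the 4.2 minimum and pre-discharge scan. The number of patients affected is unknown and likely small, being a fraction of an event count that is itself below one at the rates from the participating centres.

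Two assumptions matter. First, some sites may work from 4.5 rather than 4.2; the protocol gives no information on this. Second, the procedure after which 4.5 places its repeat echo is taken to be the biopsy, as in 3.1 and 3.5.b. If it meant the whole catheterization, a scan would follow the later procedures, but there would still be no minimum stay and no scan in the post-procedural unit.

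**What to change.** Amend 4.5 to the 4.2 rule: at least 2 hours of observation, longer if local protocol or the operator requires it; an immediate echo; and a repeat echo in the post-procedural unit before discharge and after any later procedure. In 3.1, make the discharge sentence subject to the 4.2 minimum. Listing the pre-discharge echo in 3.5 is optional; it would give its findings a stated place.

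The cost is protocol wording and, if the option is taken, a few data fields. Some sites would have a longer stay and one more limited echo, both of which 4.2 already requires.
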